## 1.2.1 Treatment Assignment

This is a Phase II, open-label, single-arm study. Patients with both ALK fusion and selected ALK mutations will be enrolled in the study.

## 1.2.2 Blinded Independent Center Review

Scans will be sent for blinded independent center review (BICR) for assessment of responses according to RECIST v1.1 and, for patients with primary CNS tumors, according to RANO criteria.

Assessments performed by BICR will not be shared with the investigator and will have no impact on the management of the patient. Further details are included in the BICR Charter.

## 1.2.3 Data Monitoring

An internal monitoring committee (IMC) will monitor patient safety throughout the study, focusing on death cases and interim futility analysis. The IMC will include Sponsor's representatives from Clinical Science, Clinical Safety, and Biostatistics. The IMC will review all necessary cumulative data at regular intervals during the study. At the time of each review, the IMC will make appropriate recommendations (e.g., the study should continue as planned, the protocol should be amended, enrollment should be held pending further safety evaluations). Decisions will be made in consideration of the totality of the available data. Ad-hoc meetings may be called in addition to scheduled meetings, as necessary, to provide recommendations on management of any new safety issues. Specific operational details such as the Committee's composition, frequency and timing of meetings, and members' roles and responsibilities are provided in the IMC Charter.

## 2. STATISTICAL HYPOTHESES

It will be tested that the confirmed ORR is greater than 30% which is assumed to be the minimal clinically relevant response rate.

Alectinib—F. Hoffmann-La Roche Ltd Statistical Analysis Plan BO41929

## 3. SAMPLE SIZE DETERMINATION

Patients with both ALK fusion and selected ALK mutations will be enrolled in the study. Enrollment will end once around 50 patients with ALK fusions solid tumors evaluable according to RECIST v1.1 have been recruited (regardless of the number of enrolled patients with primary CNS tumors, CUP, or harboring selected ALK mutations).

This sample size has been chosen so that for the primary analysis the lower limit of the two-sided 95% confidence interval (CI) (using an exact Clopper-Pearson CI) around the point estimate of the confirmed ORR according to RECIST v1.1 will represent a clinically relevant response. With a sample size of 50 patients, an observed response rate of 46% (23 of 50 responses) would have a lower limit of the two-sided 95% CI of 31.8%, which is considered to be clinically relevant in this tissue-agnostic, biomarker-defined population with no available treatment options. With 50 patients, there is 70% power to detect a 16% increase in ORR from clinically relevant 30% to 46% at the 5% two-sided significance level.

Different ORR scenarios with their associated 95% CI are presented in Table 3.

Expected ORR	Expected Number of Patients with a Response	95% CI for ORR a
46%	23	(31.81%, 60.68%)
48%	24	(33.66%, 62.58%)
50%	25	(35.53%, 64.47%)

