## 5.3 PRIMARY ENDPOINT ANALYSIS

## 5.3.1 Definition of Primary Endpoint

The primary efficacy endpoint is confirmed ORR as determined by the investigator in patients with ALK fusion solid tumors (excluding enrolled patients with CUP and CNS primary tumors). An objective response is defined as a CR or a PR according to RECIST v1.1. Confirmation of objective response is required (confirmed ≥ 28 days apart in two separate tumor assessments). Patients not meeting this criterion (including patients without a post-baseline tumor assessment) will be considered as non-responders. ORR is defined as the proportion of patients with measurable disease at baseline who have an objective response in the response-evaluable population.

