# 5.3.2 Main Analytical Approach for Primary Endpoint

An estimate of the confirmed ORR and its two-sided 95% CI using the Clopper-Pearson method will be calculated. The confirmed ORR will be tested against the minimal clinically relevant ORR of 30% in this tissue-agnostic, biomarker-defined population with no available treatment options at the 5% two-sided significance level, i.e., the lower limit of the Clopper-Pearson CI must be bigger than 30%.

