# 5.8 INTERIM ANALYSES

A non-binding interim analysis will be performed after 15 RECISTv1.1 investigatorassessed response-evaluable patients with ALK fusions tumors (excluding patients with primary CNS tumors and patients with solid tumors of CUP) have at least a responseevaluation available at 8 weeks (unless they progressed or discontinued earlier from the study). During the period waiting for a response evaluation of these first 15 patients, the study will continue to enroll. If the analysis result shows that the response rate does not achieve at least 25% (4 responders), the study may be terminated due to futility.

Further details regarding the rules and guidelines of data review will be provided in the IMC Charter.

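### The stated 70% power does not belong to the planned exact test, which has about 55% power at a true ORR of 46% with 50 patients

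*SAP*

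**What the plan says.** SAP Section 2 states the hypothesis: "It will be tested that the confirmed ORR is greater than 30% which is assumed to be the minimal clinically relevant response rate". Section 5.3.2 gives the decision rule for the two-sided 5% test: "the lower limit of the Clopper-Pearson CI must be bigger than 30" percent.

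SAP Section 3 bases the sample size on the exact interval, noting that "an observed response rate of 46% (23 of 50 responses) would have a lower limit of the two-sided 95% CI of 31.8" percent. It then adds: "With 50 patients, there is 70% power to detect a 16% increase in ORR from clinically relevant 30% to 46" percent, "at the 5% two-sided significance level". The sentence names no test or approximation. Protocol 6.1 and the sample size part of the synopsis carry the same statement.

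The final number is not fixed exactly: "Enrollment will end once around 50 patients with ALK fusions solid tumors evaluable according to RECIST v1.1 have been recruited". On missing data, SAP 5.3.1 says: "Patients not meeting this criterion (including patients without a post-baseline tumor assessment) will be considered as non-responders". The denominator therefore stays at the full response-evaluable set.

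**The concern.** The SAP's own table of ORR scenarios shows the problem. It lists 23 as the expected number of responders at an ORR of 46%, and 23 is also the smallest count that passes the decision rule. When the pass mark equals the expected count, the chance of passing must be close to one half. A claim of 70% cannot fit that rule.

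Power is the main planning property of the primary test. A reader who sees an exact interval justifying the sample size, an exact interval as the decision rule and a power figure between them will take the power to be that of the exact rule. That reader would put the risk of failing with an active drug at 30%, when it is about 45%.

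**Working it through.** **Inputs.** n = 50 (SAP 3); null ORR p0 = 0.30 (SAP 2 and 5.3.2); planned ORR p1 = 0.46 (SAP 3); two-sided level 5%, so 2.5% in the upper tail (SAP 3 and 5.3.2); success if the Clopper-Pearson lower limit exceeds 30% (SAP 5.3.2).

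**Step 1: reproduce the 70%.** Use a one-sample normal approximation with the null variance throughout:

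- Standard error under the null: √(0.30 × 0.70 / 50) = 0.0648.
- Power = Φ((0.46 − 0.30)/0.0648 − 1.96) = Φ(2.469 − 1.960) = Φ(0.509) = 69.5%.

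Using the null variance for the critical value and the alternative variance for power gives 68.0%. Other two-sided approximations give less: 62.2% with the alternative variance only, 62.8% with a continuity correction and 64.9% with the arcsine transformation. The plan's figure is thus consistent with a large-sample z-test.

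**Step 2: find the pass mark under the planned rule.** The Clopper-Pearson lower limit for x responders is the 2.5% quantile of a Beta(x, n − x + 1) distribution.

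| Responders of 50 | Lower limit | P(X ≥ x) at ORR 30% | P(X ≥ x) at ORR 46% |
|---|---|---|---|
| 21 | 28.19% | 4.78% | 76.0% |
| 22 | 29.99% | 2.51% | 66.3% |
| 23 | 31.81% | 1.23% | 55.5% |
| 24 | 33.66% | 0.56% | 44.2% |

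The limits for 23 and 24 match the SAP's own table. At 22 the lower limit is 29.991% and the upper tail probability is 0.02509, just above 0.025, so 22 fails. Success needs at least 23.

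**Step 3: exact power of that rule.** P(X ≥ 23 | n = 50, p = 0.46) = 0.5548. The shortfall is 70 − 55.5 = 14.5 points. The probability of missing the objective is 1 − 0.555 = 44.5%, against the implied 30%. The exact one-sided type I error is 1.23%.

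**Step 4: what would give 70%.** With the pass mark at 23 of 50, power is 66.4% at a true ORR of 48% and 76.0% at 50%. It reaches 70% at a true ORR of about 48.7% and 80% at about 51.0%.

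**Step 5: allow for a final number near 50.** Repeating steps 2 and 3 at a true ORR of 46%:

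| n | Pass mark | Exact power |
|---|---|---|
| 48 | 22 | 56.5% |
| 49 | 22 | 61.6% |
| 50 | 23 | 55.5% |
| 51 | 23 | 60.5% |
| 52 | 23 | 65.2% |
| 55 | 24 | 68.6% |
| 57 | 25 | 67.5% |
| 58 | 25 | 71.6% |

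No n from 44 to 57 reaches 70%; the first that does is 58.

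**Step 6: the interim.** SAP 5.8 says that with fewer than 4 responders among the first 15, "the study may be terminated due to futility". If that rule were always followed, and if responders at the interim are taken as final confirmed responders, power at 46% falls slightly, to 55.1%. The rule is non-binding, and interim responses need not yet be confirmed, so this figure is only indicative.

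**The case against.** The best defense is that 70% is not a slip of arithmetic. The power sentence names no test, and a standard normal approximation gives 69.5%. That is true, and it explains where the number probably came from. It does not justify it, because SAP 5.3.2 fixes a different test and Section 3 itself argues from the exact interval.

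Second, 55.5% is a low point in a sawtooth. At n = 50, 22 responders miss by 0.009 percentage points, and power is higher at 49, 51 and 52. This stands as a reason to quote a range, but the range for 48 to 52 is 55% to 65% and stays below 70%. Even counting 22 of 50 as a success would give only 66.3%.

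Third, the sample size is justified mainly by the interval, whose table is correct, and nothing in the analysis changes. This limits the consequence: the estimate, the interval and the type I error are sound. But the plan states a hypothesis and a pass/fail rule, and gives the power figure in three places, so it is a formal claim that should be true.

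**Conclusion.** The concern holds. Under the rule in SAP 5.3.2, 50 patients give 55.5% power at a true ORR of 46%, not 70%. The stated figure is an approximate power for a z-test that the plan does not use. For a final number between 48 and 52, exact power is 55% to 65%.

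The result rests only on figures in the documents: n = 50, rates of 30% and 46%, and the Clopper-Pearson rule. It assumes independent patients with a common response probability and no early stop for futility. This is an error in a stated planning property. It does not bias the primary analysis or inflate its error rate, which is 1.23% one-sided against a nominal 2.5%.

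**What to change.** In SAP Section 3, Protocol 6.1 and the synopsis, replace the power sentence with text to this effect: With 50 patients the primary test succeeds with at least 23 responders (22 of 50 has a lower limit of 29.99%). The exact one-sided type I error is 1.2%, and exact power is about 55% at a true ORR of 46%, 66% at 48% and 76% at 50%. It would help to add that, for a final number of 48 to 52, power at 46% is between 55% and 65%.

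Enrollment, the success rule and the analysis need no change. The cost is one sentence in each place and a less favorable power figure. The protocol text has to go through the amendment process in Protocol 9.7. SAP 5.1 says its analyses supersede the protocol's for a regulatory filing, so the SAP could be corrected first and the protocol aligned at its next amendment.

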#### Table 3 ORR Scenarios with Associated 95% CI

CI=confidence interval; ORR=objective response rate.

a Using the Clopper-Pearson method and given a sample size of 50 patients.

With a sample size of 50 patients, an ORR of 46% will have an associated 95% CI of 31.81% to 60.68%.

## 4. ANALYSIS SETS

The following populations are defined:

Population	Definition
Response-evaluable population	All patients with ALK fusion-positive solid tumors (excluding patients with CUP and primary CNS tumors) with measurable disease at baseline (who have a baseline tumor assessment) per the investigator according to RECIST v1.1 and have received at least one dose of study treatment.
Response-evaluable population with measurable CNS disease at baseline	All patients with measurable CNS disease at baseline evaluable per the investigator according to RECIST v1.1 who have received at least one dose of study treatment.
Primary CNS tumor response-evaluable population	All patients with ALK fusion CNS primary tumors with measurable disease at baseline evaluable according to RANO criteria who receive at least one dose of study treatment.
CUP response-evaluable population	All patients with CUP with measurable disease at baseline evaluable according to RECIST v1.1 who receive at least one dose of study treatment.
ALK-mutations response- evaluable population	All patients with ALK mutations with measurable disease at baseline evaluable according to RECIST v1.1 who receive at least one dose of study treatment.
Exploratory ALK-positive CUP and non-CUP response-evaluable population	All patients with ALK-positive CUP and non-CUP solid tumors who receive at least one dose of study treatment.
Responders	All patients with a response according to the specified endpoints for the analysis of the duration of response
PK-evaluable population	All patients who received any dose of study medication and who have at least one post-baseline PK sample available.
Safety-evaluable	All participants who received at least one dose of study treatment.

#### Table 4 Analysis Populations

ALK=anaplastic lymphoma kinase; CUP=cancer of unknown primary (site); CNS=central nervous system; PK=pharmacokinetic; RANO=Response Assessment in Neuro-Oncology; RECIST v1.1=Response Evaluation Criteria in Solid Tumors, Version 1.1.

All populations that are defined accordingly by the investigator assessment are defined in the same way by BICR, depending on who is assessing the endpoint.

Replacement of patients with ALK fusion solid tumors assessed according to RECIST v1.1 who discontinue their participation in the study will be allowed if enrolled patients have not received any dose of alectinib.

All patients must have measurable disease at baseline as assessed by investigator according to the inclusion criteria. Therefore, progression free survival (PFS) and overall survival (OS) will be assessed in the response-evaluable populations of the patients with

the respective disease characteristics. For PFS analyses by BICR the population defined by the investigator is taken into account.

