4.1.1 Inclusion Criteria

Patients must meet the following criteria for study entry:

- Signed Informed Consent Form
- Age ≥ 18 years at time of signing Informed Consent Form
- Histologically confirmed locally advanced or metastatic solid tumor excluding lung cancer
- ALK-positive tumor per FMI NGS (NGS F1CDx, F1LCDx, or F1HEME) or per local accredited laboratory using validated NGS testing of tumor tissue or peripheral blood:
 - ALK fusion
 - The following ALK-activating mutations: R1275Q, F1245C, or F1174X
 - Local ALK test report (only for cases with local ALK testing; see Section 4.6.5.3)
- Disease progression on prior treatment, or previously untreated disease with no available acceptable treatment
- Other prior cancer therapies are allowed, including investigational drugs, if any treatment-related toxicities (excluding alopecia) have resolved to Grade 1 or better and laboratory values as defined in inclusion criteria, and meet the following washout criteria prior to first dose of alectinib:
 - At least 4 weeks must have elapsed since the last dose of the prior cytotoxic chemotherapy or antibody-directed therapy.
 - At least 7 days must have elapsed since prior tyrosine kinase inhibitor (TKI) therapy.
 - At least 14 days must have elapsed since prior radiotherapy.
- Measurable disease at baseline, as assessed by investigator (by RECIST v1.1, or according to RANO criteria for patients with primary CNS tumors)
 - For primary CNS tumors, only MRI scans will be accepted. If the local radiology facility cannot perform MRI, the patient will be excluded from the study.
- Life expectancy of at least 12 weeks in the opinion of the investigator
- Eastern Cooperative Oncology Group (ECOG) Performance Status of 0–2 (see Appendix 3)
- Adequate hematologic function:
 - Platelet count \geq 100 \times 10⁹/L
 - Absolute neutrophil count \geq 1500/µL
 - Hemoglobin \geq 9 g/dL
- Adequate hepatic function:
 - ALT (SGPT) and AST (SGOT) $\leq 2.5 \times$ upper limit of normal (ULN) ($\leq 5 \times$ ULN for patients with concurrent liver metastasis)
 - Bilirubin ≤2 mg/dL

Alectinib—F. Hoffmann-La Roche Ltd 42/Protocol BO41929, Version 4

- Adequate renal function:
 - Serum creatinine $< 2 \times ULN$
 - Calculated creatinine clearance of ≥ 60 mL/min (Cockcroft-Gault formula)
- Patients with primary CNS tumors are eligible
- Patients with CUP tumors are eligible

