6. STATISTICAL CONSIDERATIONS AND ANALYSIS PLAN

The following populations are defined:

- The response-evaluable population is defined as all patients with ALK fusion (excluding patients with CUP and CNS primary tumors) solid tumors with measurable disease at baseline evaluable according to RECIST v1.1 who receive at least one dose of study drug.
- All populations are defined according to the investigator or by blinded independent center review (BICR), depending on who is assessing the endpoint.
- The response-evaluable population with measurable CNS disease at baseline is defined as all patients with measurable CNS disease at baseline evaluable according to RECIST v1.1 who receive at least one dose of study drug.
- The primary CNS tumor response-evaluable population is defined as all patients with ALK fusion CNS primary tumors with measurable disease at baseline evaluable according to RANO criteria who receive at least one dose of study treatment.
- The CUP response-evaluable population is defined as all patients with CUP with measurable disease at baseline evaluable according to RECIST v1.1 who receive at least one dose of study drug.
- The ALK-mutations response-evaluable population is defined as all patients with ALK mutations with measurable disease at baseline evaluable according to RECIST v1.1 who receive at least one dose of study drug.

The primary analysis will be performed on the response-evaluable population.

Secondary analyses will be performed on the response evaluable population, the measurable CNS disease at baseline response-evaluable population, the primary CNS tumor response evaluable population, the CUP response-evaluable population, and the ALK mutation response-evaluable population, separately. The DOR will be assessed in the patients with confirmed or unconfirmed objective response, as appropriate.

Alectinib—F. Hoffmann-La Roche Ltd

Safety analyses will be performed on all enrolled patients who receive at least one dose of study drug.

Details of all above analyses will be provided in the Statistical Analysis Plan.

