# 5. STATISTICAL ANALYSES

## 5.1 GENERAL CONSIDERATION

The analyses outlined in this statistical analysis plan (SAP) supersede those specified in the protocol for the purpose of a regulatory filing.

ORR, duration of response (DOR), and PFS are determined by the investigator and by BICR according to RECIST v1.1 and RANO respectively. Secondary endpoint analyses for the endpoint by BICR are as well sensitivity analyses for that endpoint by investigator.

CNS ORR and DOR are determined in patients with CNS metastases at baseline only by BICR according to RECIST v1.1.

The analyses will be performed in the populations specified in Section 4.

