## 5.4 SECONDARY ENDPOINTS ANALYSES

## 5.4.1 Key Secondary Endpoint

The key secondary efficacy endpoint is confirmed ORR as determined by the BICR in patients with ALK fusion solid tumors (excluding enrolled patients with CUP and CNS primary tumors). The same analyses as for the primary endpoint will be applied.

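### The key secondary BICR response rate uses a BICR-defined denominator, so it can be biased upward relative to the primary population and is not a clean sensitivity analysis of the primary endpoint

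*SAP*

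**What the plan says.** Eligibility requires "Measurable disease at baseline, as assessed by investigator" (Protocol 4.1.1), and Protocol 9.5 says independent review is not used for eligibility. SAP Table 4 defines the response-evaluable population by the investigator's finding of measurable disease plus at least one dose.

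For endpoints read by BICR, the text under SAP Table 4 says: "All populations that are defined accordingly by the investigator assessment are defined in the same way by BICR", with the choice between the two following the reader of the endpoint. Protocol Section 6 has the same rule: "All populations are defined according to the investigator or by blinded independent center review (BICR), depending on who is assessing the endpoint". The secondary objective in the synopsis and in Protocol 2.1.2 repeats it. The SAP then makes one exception: "For PFS analyses by BICR the population defined by the investigator is taken into account". ORR is not excepted.

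SAP 5.4.1 states: "The key secondary efficacy endpoint is confirmed ORR as determined by the BICR". It adds: "The same analyses as for the primary endpoint will be applied". By SAP 5.3.2 that means a Clopper-Pearson interval whose lower limit must exceed 30%. SAP 5.3.3, on sensitivity analyses of the primary endpoint, only refers back to SAP 5.1, which says: "Secondary endpoint analyses for the endpoint by BICR are as well sensitivity analyses for that endpoint by investigator".

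In SAP Table 2 the main secondary estimand is described only as being according to BICR. Its population is not restated.

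**The concern.** The primary endpoint is read by the investigator in an open-label, single-arm study. The BICR ORR is the one sensitivity analysis that the SAP provides for it. To serve that purpose it should change the reader and hold the patients fixed. Under the Section 4 rule it changes both, so a gap between the two rates cannot be attributed to the reader. Agreement between them could likewise hide a difference.

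The direction is foreseeable. Appendix 5, Table 2 of the protocol (non-target disease only) allows complete response, non-CR/non-PD, not evaluable or progression, but no partial response. A patient in whom BICR finds no measurable lesion can be a BICR responder only through a complete response. The patients removed are therefore mostly patients who would otherwise count as non-responders. The rule that counts unconfirmed or unassessed patients as non-responders applies only inside the denominator, and neither document says how the removed patients are counted or reported.

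**Working it through.** **Inputs.** N = 50, null rate 30% and the rule that the lower limit must exceed 30% (SAP Sections 2, 3 and 5.3.2). The number k of patients whom BICR finds non-measurable is not in the documents. I take k = 0 to 6 and assume that all of them are non-responders.

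**Plan's own figure.** The Clopper-Pearson lower limit for x of n is the 2.5% quantile of Beta(x, n − x + 1); the upper limit is the 97.5% quantile of Beta(x + 1, n − x). For 23/50 this gives 31.81% to 60.68%, which matches SAP Table 3.

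**Effect on the pass mark.** With all 50 kept, 22/50 = 44.0% has a lower limit of 29.99% and fails, so 23 responders are needed. Dropping non-responders lowers that number:

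| BICR responders | Lower limit with n = 50 | Fewest dropped to pass | Lower limit then |
|---|---|---|---|
| 22 | 29.99% (fails) | 1 (22/49 = 44.9%) | 30.67% (passes) |
| 21 | 28.19% (fails) | 3 (21/47 = 44.7%) | 30.17% (passes) |
| 20 | 26.41% (fails) | 6 (20/44 = 45.5%) | 30.39% (passes) |

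**Effect on the estimate.** With 23 BICR responders the rate is 23/50 = 46.0%, 23/49 = 46.9% with one dropped, 23/47 = 48.9% with three and 23/45 = 51.1% with five.

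**Chance of passing.** Suppose the true BICR ORR over all 50 is 30%, which is 15 expected responders, all among the n = 50 − k patients kept. The rate among those kept is 15/n. With r the minimum number of responders that passes at that n, the chance of passing is P(X ≥ r), X ~ Binomial(n, 15/n). The last column replaces 15/n by 30%, the null for the BICR-measurable subset itself.

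| k | n | r | 15/n | Chance of passing, 30% over all 50 | Chance of passing, 30% within subset |
|---|---|---|---|---|---|
| 0 | 50 | 23 | 30.0% | 1.2% | 1.2% |
| 1 | 49 | 22 | 30.6% | 2.45% | 1.95% |
| 2 | 48 | 22 | 31.3% | 2.39% | 1.48% |
| 3 | 47 | 21 | 31.9% | 4.5% | 2.35% |
| 6 | 44 | 20 | 34.1% | 7.8% | 2.18% |

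The nominal upper-tail level is 2.5%. Using Binomial(50, 0.30) for the responder count instead gives 2.5% for k = 1 or 2 and 4.8% for k = 3, so the pattern does not depend on that modelling choice.

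**The case against.** The rule is pre-specified, disclosed and the same in both documents. Restricting a RECIST response rate to patients whom the same reader finds measurable is a defensible choice. A different set for BICR PFS is not in itself an inconsistency, because progression can be scored from new or non-target lesions. All of this stands, and it is why the present denominator should survive as a supplementary estimate. It does not answer the main point: a defensible BICR rate in its own population is still not a sensitivity analysis of the primary estimand.

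A reader might infer three stronger things that the documents do not support.

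- *The BICR rate is inflated.* Every enrolled patient should already have investigator-measurable disease, and no document gives a reclassification rate. If BICR agrees on everyone, the two denominators coincide. The BICR Charter, which is not available here, may also deal with baseline non-measurability.
- *The test has an inflated type I error.* For the BICR-measurable subset's own null it stays below 2.5% throughout the table. The excess arises only when the null is set over all 50 patients, and not before three non-responders are dropped.
- *A trial decision turns on it.* SAP 5.3.2 states the success rule for the primary endpoint. SAP 5.4.1 reuses the analysis, but no hierarchy or decision is tied to its result. The one-patient reversal also needs exactly 22 responders in 50, which has probability 10.9% at a true rate of 46% and 1.3% at 30%.

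Nor is BICR ORR the only BICR analysis: duration of response and PFS are also read by BICR. It is, however, the only sensitivity analysis of the response rate.

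**Conclusion.** The point holds in conditional form. As written, treated fusion patients whom BICR finds non-measurable leave the BICR ORR denominator. The rate can then be biased upward relative to the primary population, and reader and population effects cannot be separated.

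The size depends on an unknown count. It is nil if no one is reclassified. One reclassified patient is enough to reverse the 30% comparison at 22 responders. Measured against a true 30% over all 50 patients, the chance of passing rises from 1.2% to about 2.4% with one or two dropped, 4.5% with three and 7.8% with six. These figures assume that every dropped patient is a non-responder; a BICR complete response among them would reduce the effect.

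I am confident about what the rule says and about the expected direction, but not about the magnitude. The change should be made before any BICR data are analysed.

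**What to change.** In SAP Sections 4 and 5.4.1, extend the existing PFS exception to ORR: analyse BICR ORR in the investigator-defined response-evaluable population. Count patients without BICR-measurable disease as non-responders unless they have a confirmed BICR complete response, which Appendix 5, Table 2 of the protocol allows. Counting all of them as non-responders would bias the rate downward.

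Report how many such patients there are, and keep ORR on the BICR-measurable denominator as a supplementary estimate. State the population for the main secondary estimand in SAP Table 2.

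Align the protocol wording in the synopsis, Section 2.1.2 and Section 6. SAP 5.1 lets the SAP supersede the protocol only for a regulatory filing, so changing the SAP alone would leave the two documents in conflict.

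The cost is a few sentences, one extra table and possibly a slightly lower key secondary estimate. No new data and no change to study conduct are needed.
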